3 STUDY DESIGN

3.1 Study Phase

Study phase: Phase I/II

3.2 Study Design

A randomized, multicenter, observer-blinded, placebo-controlled study with Japanese male and female subjects who are seronegative for SARS-CoV-2 antibodies and negative for SARS-CoV-2 PCR test at screening.

125 subjects will be randomized 4:1 and will receive the same 3.75 μ g of MT-2766 or placebo. Subjects will receive two intramuscular (IM) injections 21 days apart on Days 0 and 21, into the deltoid region of the alternating arm (each arm will be injected once), of one of the following blinded treatments:

- ◆ Group 1: 3.75 μ g of MT-2766 in a final volume of 0.5 mL (n=100)
- ◆ Group 2: Placebo for MT-2766 3.75 μ g in a final volume of 0.5 mL (n=25)

In addition, subjects in Group 3 (n=20) will receive two IM injections of 1.875 μ g MT-2766 21 days apart on Days 0 and 21, into the deltoid region of the alternating arm (each arm will be injected once) under open-label. The study may be completed even if fewer than 20 subjects in Group 3 are enrolled.

[figure not shown]
- ◆ Group 3: 1.875 μ g of MT-2766 in a final volume of 0.25 mL (n=20)

Subjects will be screened up to 21 days in advance of the first vaccine administration and will demonstrate a satisfactory baseline medical assessment by history, general physical examination, hematological, biochemical, urinalysis and serological analysis. Although tests for SARS-CoV-2 antibodies and PCR will be performed at screening, negative subjects will be enrolled. On Day 0 and Day 21, vaccine administration will occur. Phone contacts will be made after each vaccine administration, specifically for review of the subject's safety and concomitant medication data. Visits to the study site will occur 3 days after each vaccine administration for key safety assessments, and 21 days after each vaccine administration for key safety and immunogenicity assessments.

Subjects will return to the study site on Day 128, Day 201, and Day 386 (3-month, 6-month, and 12-month safety follow-ups and immunogenicity assessments after the last vaccine administration).

In Group 1 and Group 2, the randomization code will be opened after data lock when all subjects in Groups 1 and 2 have reached Day 42. Once the study is unblinded, if the efficacy may be inadequate or unconfirmable, public vaccination will be allowed in Group 1 (3.75 μ g of MT-2766). Once the study is unblinded, public vaccination will be allowed in Group 2 (placebo group). In these cases the subject will be withdrawn from the study.

In Group 3, if the efficacy may be inadequate or unconfirmable, public vaccination will be recommended. In this case the subject will be withdrawn from the study.

3.3 Schedule for Tests and Observations

Table 1 shows the parameters of tests and observation, and the schedule.

Table 1 Time and Events Schedule

	Days -21 to Day -1 (screening)	Day 0	Day 1 (+1)	Day 3 (±1)	Day 8 (±1)	Day 15 (±1)	Day 21 (±2) ¹³	Day 22 (±1)	Day 24 (±1)	Day 29 (±2)	Day 36 (±2)	Day 42 (±2)	Day 49 (±2)
Visit Number	1	2	Phone ¹²	3	Phone ¹²	Phone ¹²	4	Phone ¹²	5	Phone ¹²	6	Phone ¹²	
Informed consent	X												
Demographics	X												
Medical history /Complications	X	X											
Prior medication	X	X											
Inclusion/Exclusion criteria	X	X											
Randomization (for Groups 1&2)	X	X											
Vaccine administration		X					X						
Physical examination	X	X	X	X	X	X	X	X	X	X	X	X	X
Vital signs ¹	X	X	X	X	X	X	X	X	X	X	X	X	X
Height/screening only/Weight/BMI	X	X											
SARS-CoV-2 PCR test	X												
SARS-CoV-2 antibody test ²	X												
Blood chemistry ³ /Hematology ⁴	X	X	X	X	X	X	X	X	X	X	X	X	X
Urinalysis ⁵	X	X					X	X	X	X	X	X	X
HIV/HBV/HCV	X						X						
Pregnancy test ⁶	X ⁵	X					X						
Immunogenicity - Serology (Nab assay/ ELISA/ anti-plant glycans IgE antibodies) ⁷	X						X						X
Immunogenicity - CMI response ((ELISpot and ICS) ⁸	X						X						X
Immediate surveillance		X						X					
Provide and collect paper diary and memory aid ⁹		X		X			X		X		X		X
Collection of solicited local/systemic AEs		X	X	X	X			X	X	X	X		
Concomitant medications ¹⁰													
AEs, SAEs, AESIs, MAAEs ¹¹													
Collection of COVID-19 symptoms													

Subject(s) will be instructed to contact the study site if they experience symptoms of COVID-19 from the day of the first vaccination (Day 0, post vaccination) until the end of the study.

Confidential

Page 11 of 60

Statistical Analysis Plan for Final Analysis
Protocol No. MT-2766-A-101 (CP-PRO-CoV1P-028)

	Day 77 (±14) Phone ¹²	Day 105 (±14) Phone ¹²	Day 128 ¹⁴ (±14) Phone ¹²	Day 161 (±14) Phone ¹²	Day 189 (±14) Phone ¹²	Day 201 (±14) Phone ¹²	Day 245 (±14) Phone ¹²	Day 273 (±14) Phone ¹²	Day 301 (±14) Phone ¹²	Day 329 (±14) Phone ¹²	Day 357 (±14) Phone ¹²	Day 386 (±14) Phone ¹²
Visit Number												
Informed consent												
Demographics												
Medical history /Complications												
Prior medication												
Inclusion/Exclusion criteria												
Randomization												
Vaccine administration												
Physical examination												
Vital signs ¹												
Height (screening only)/Weight/BMI												
SARS-CoV-2 PCR test												
SARS-CoV-2 antibody test ²												
Blood chemistry ³ /Hematology ⁴												
Urinalysis ⁵												
HIV/HBV/HCV												
Pregnancy test ⁶												
Immunogenicity -Serology (Nab assay// ELISA/ anti-plant glycans IgE antibodies) ⁷												
Immunogenicity - CMI Response (ELISpot and ICS) ⁸												
Immediate surveillance												
Provide and collect paper diary and memory aid ⁹												
Collection of solicited local/systemic AEs												
Concomitant medications ¹⁰												
AEs, SAEs, AESIs, MAAEs ¹¹												
Collection of COVID-19 symptoms												

Subjects will be instructed to contact the study site if they experience symptoms of COVID-19 from the day of the first vaccination (Day 0, post vaccination) until the end of the study.

- 1) Resting blood pressure (BP), pulse rate (PR), respiratory rate (RR), and body temperature.
- 2) Anti-N antibodies will be measured at screening, Days 201 and 386.
- 3) Biochemistry (serum): Sodium, Potassium, Urea, Creatinine, Glucose, Bilirubin (total), Albumin, Total protein, Alkaline phosphatase, Alanine aminotransferase (ALT), Aspartate aminotransferase (AST), Gamma glutamyl transferase (GGT), Cholesterol (total, HDL, LDL), Triglycerides, Chloride, Calcium, Phosphorus.

- 4) Hematology: Hemoglobin, Hematocrit, Red blood cells, Platelets, Mean platelet volume (MPV), Neutrophils, Mean cell hemoglobin (MCH), Mean corpuscular hemoglobin concentration (MCHC), Mean cell volume (MCV), White cell count (total, WBC), Lymphocytes, Monocytes, Eosinophils, Basophils
- 5) Urinalysis: Macroscopic examination (color, clarity), pH, Specific gravity, Glucose, Protein, Occult blood
- 6) It will be tested in serum at screening and in urine at Days 0, 21, 42, and 128.
- 7) On Days 21 and 128, the immunogenicity- serology blood sample will be collected for the Nab assay and ELISA only. Anti-plant glycan IgE antibodies will only be measured on Days 0, 42, 201 and 386.
- 8) Blood samples may not be collected for all subjects.
- 9) If subject cannot use electronic diary, paper diary and memory aid will be acceptable.
- 10) From Day 43, concomitant medication collection will be limited to those used to treat an SAE, medically attended adverse event (MAAE), AE leading to withdrawal, AEs of special interest (AESIs), or an AE that occurred before Day 42 and that is still being used afterwards (i.e. on-going use).
- 11) AEs will be collected up to Day 49; SAEs, MAAEs, AESIs will be collected through to the end of the study.
- 12) The study site should contact the subject via the electronic diary, phone, fax or email.
- 13) All efforts will be done to have subjects returning on planned date for Day 21 activities. If for any reason the visit is done before or after this planned date, subsequent visits/procedures will be adjusted accordingly.
- 14) Any subject who withdraws the study will be asked to undergo Day 128 visit procedures within two weeks of withdrawal, if the subject agrees. If a subject is withdrawn from Day 1 to Day 29, solicited local/systemic AEs are including. If a subject is withdrawn from Day 1 to Day 49, unsolicited AEs are investigated. If deemed necessary by (sub)investigator, necessary tests such as biochemistry, hematology, or urinalysis will be performed.

3.4 Sample Size and Power Considerations

The sample size is not based on a formal statistical power calculation but was considered to be adequate to meet the objectives of the study.

4 PLANNED ANALYSIS

4.1 Interim Analysis

Interim analyses for immunogenicity and safety will be conducted by MTPC after interim database lock up to Day 42 data in Group 1 and Group 2.

4.2 Final Analysis

The database will be locked twice. One is the interim database lock for the above-mentioned interim analyses (see Section 4.1), and the other is the final database lock for the final analyses. The SAP will be finalized and signed off prior to each database lock. Final data analysis will be conducted after the final database lock.

5 ANALYSIS SET

The statistical analysis will be based on separate analysis sets, defined as follows:

Safety Analysis Set (SAS): All subjects who received at least one dose of either the MT-2766 or placebo.

Immunogenicity Intent-to-treat (ITT) Set All subjects who receive at least one dose of either the MT-2766 or placebo and who have at least 1 post-baseline Immunogenicity assessment.

Immunogenicity Per Protocol (PP) Set Immunogenicity ITT set who do not have any major protocol violations, and who received either the MT-2766 or placebo. For the Day 21 analysis, this should include the subjects who received the first vaccine dose and had Day 0 and Day 21 immunogenicity sample collections. For the Day 42 analysis, this should include the subjects who received both vaccine doses and had Day 0 and Day 42 immunogenicity sample collections. For the Day 128 analysis, this should include the subjects who received both vaccine doses and had Day 0 and Day 128 immunogenicity sample collections. For the Day 201 analysis, this should include the subjects who received both vaccine doses and had Day 0 and Day 201 immunogenicity sample collections.

All safety analyses will be performed using the SAS. The analyses of all immunogenicity endpoints will be performed using the Immunogenicity PP set as the primary analysis population, and the immunogenicity ITT set, as a secondary analysis population.

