2.2.2 Secondary Endpoints

The following secondary safety and immunogenicity endpoints are for Groups 1 and Group 2.

Safety:

1. The incidences of SAEs, MAAEs, AEs leading to withdrawal, AESIs, and deaths from Day 43 to Day 201;
2. The incidences of SAEs, MAAEs, AEs leading to withdrawal, AESIs, and deaths from Day 202 to Day 386;
3. The numbers and percentages of subjects with normal and abnormal urine, hematological, and biochemical test results within three days of first (Day 0) and second (Day 21) injections.

Immunogenicity:

1. Persistence of SARS-CoV-2 Nab response will be assessed on Days 128, 201, and 386 using the following parameters: GMT, SC rate, and GMFR.
2. SARS-CoV-2-specific antibody responses will be measured on Days 0, 21, and 42 based on the total immunoglobulin G (IgG) level, and the persistence of these antibodies will be analyzed on Days 128, 201, and 386 using the following parameters: GMT, SC rate, and GMFR;
3. SARS-CoV-2-specific Th1 CMI responses will be measured on Days 201 and 386 using the IFN- γ ELISpot assay;
4. SARS-CoV-2-specific Th2 CMI responses will be measured on Days 201 and 386 using the IL-4 ELISpot assay;

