7.1.2.3 Seroconversion (SC) Rate

SC rate is defined as the proportion of subjects achieving SC in the analysis set i.e. subjects with:

- For subjects with detectable Nab/IgG titer at Day 0 (i.e. baseline Nab/IgG titer ≥ 10): a ≥ 4 -fold increase in Nab/IgG titers between Day 0 and Day 21/42/128/201, respectively.
- For subjects with undetectable Nab/IgG titer at Day 0 (i.e. baseline Nab/IgG titer < 10): Nab/IgG titer of ≥ 40 on Day 21/42/128/201, respectively.

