7.2 Analysis Visit Definitions

The date of the first vaccination is defined as Day 0.

For the Day 21 visits, a window of +/- 2 days will be applied to sample collection data. For the Day 24 visits, a time window is +/- 1 days from the date of vaccination 2 + 3. For the Day 42 visits, a time window is +/- 2 days from the date of vaccination 2 + 21. For the Day 128 visits, a time window is +/- 14 days from the date of vaccination 2 + 107. For the Day 201 visits, a time window is +/- 14 days from the date of vaccination 2 + 180. Subjects who have blood samples for immunogenicity taken outside of the time window for blood sample collection are to be excluded from the IPP set for the specific visit.

Unless otherwise specified, baseline will be the last observed value of the parameter of interest prior to the first vaccination. For post-baseline visit, if there are multiple data in a window, the later data will be used.

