7.3 Data Handling Convention for Missing Data

Concomitant medication:

There is no imputation for completely missing dates.

Missing or partial concomitant medication start date:

- If only DAY is missing, use the first day of the month.
- If DAY and Month are both missing, use the first day of the year.

Missing or partial concomitant medication stop date:

- If only DAY is missing, use the last day of the month.
- If DAY and Month are both missing, use the last day of the year.
- If DAY, Month and year are all missing, assign ‘continuing’ status to stop date.

Immunogenicity:

Missing immunogenicity data will be retained as missing.

Adverse events:

There is no imputation for completely missing dates.

Missing or partial AE date:

No imputation of AE partial/missing start/end dates or times will be performed. In case of missing or incomplete AE onset date/time, the AE will be included in the analysis unless the incomplete AE onset date/time information unequivocally indicates that the AE started prior to Day 0.

If an AE allocation to a reporting cannot be unequivocally ascertained due to partial/missing date, the AE will be allocated to all relevant periods.

Missing relatedness and intensity of AEs will not be imputed and will be presented as “Missing”.

Other safety:

For safety summaries, only observed data will be used. Unless otherwise specified, missing safety data will not be imputed.

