8.2.2 Secondary Immunogenicity Endpoints

8.2.2.1 Nab response against the SARS-CoV-2 virus

The following analyses for the Nab assay will be performed:

- GMT (Day 128 and Day 201): The point estimates and the corresponding two-sided 95 % CI by treatment group will be calculated.
- SC rate (Day 128 and Day 201): The point estimates and the corresponding two-sided 95 % CI for subjects achieving SC by treatment group will be calculated.
- GMFR: the geometric mean of the ratio of GMTs (Day 128/Day 0, Day 201/Day 0) will be calculated.

The same methodology as in section 8.2.1.1 will be used.

8.2.2.2 Specific Th1 CMI response against the SARS-CoV-2 virus measured by IFN- γ ELISpot

The specific Th1 CMI response induced on Day 201 will be analyzed according to the same methodology as in section 8.2.1.2.

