9.3 Analysis Visits to Report

Immunogenicity:

Analysis Visit	Apply to
Day 0	All immunogenicity
Day 21	All immunogenicity
Day 42	All immunogenicity
Day 128	All immunogenicity (except for CMI response)
Day 201	All immunogenicity (except for CMI response measured by the percentage of T cells)

Safety:

Analysis Visit	Apply to
Day 0	All Laboratory Tests
Day 3	All Laboratory Tests
Day 21	All Laboratory Tests
Day 24	All Laboratory Tests
Day 42	All Laboratory Tests

Analysis Visit	Analysis Time Point	Apply to	
		Vital Signs	Physical Examination
Day 0	Before vaccination	X	X
	After vaccination	X	X
Day 3		X	X
Day 21	Before vaccination	X	X
	After vaccination	X	X
Day 24		X	X
Day 42		X	X
Day 128		X	X
Day 201		X	X

Unscheduled visits, retests (same visit number assigned) and follow-up visits will not be displayed in by-visit summary tables, but will be included in the data listings.

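### Late titres (Nab at Days 128 and 201, IgG at Day 201) are kept after a SARS-CoV-2 infection that follows dose 2, and no planned immunogenicity analysis separates vaccine persistence from infection

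*SAP*

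**What the plan says.** The secondary objective is worded as persistence: "Persistence of SARS-CoV-2 Nab response will be assessed on Days 128, 201, and 386" (SAP 2.2.2). SAP 10 drops Day 386 because the study was discontinued, and SAP 8.2.2.4 plans late IgG at Day 201 only. The late endpoints in play are therefore Nab at Days 128 and 201 and IgG at Day 201.

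The rules that decide which titres count are these:

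- **Sets (SAP 5).** ITT needs one dose and one post-baseline immunogenicity assessment. PP is the "Immunogenicity ITT set who do not have any major protocol violations, and who received either the MT-2766 or placebo"; for Days 128 and 201 it also needs both doses, a Day 0 sample and the visit sample.
- **Windows (SAP 7.2).** Subjects whose samples are "taken outside of the time window for blood sample collection are to be excluded from the IPP set for the specific visit".
- **Missing data (SAP 7.3).** "Missing immunogenicity data will be retained as missing".
- **Seroconversion (SAP 7.1.2.3).** With an undetectable baseline, the criterion is "Nab/IgG titer of ≥ 40 on Day 21/42/128/201, respectively".
- **Method (SAP 8.2.2.1).** "The same methodology as in section 8.2.1.1 will be used", that is, ANOVA, Fisher's exact test and ANCOVA with baseline titre as the only covariate. IgG is handled in the same way (SAP 8.2.2.4).

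On infection markers, the schedule says "Anti-N antibodies will be measured at screening, Days 201 and 386" (SAP 3.3, footnote 2). In the analysis sections, SARS-CoV-2 antibody appears as a baseline characteristic (SAP 8.1.2) and in the safety laboratory list (SAP 8.3.3). Confirmed COVID-19 cases are recorded as adverse events (protocol 11.1.3).

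**The concern.** A titre raised by infection is not persistence of the vaccine response, yet it enters the late GMT, GMFR and seroconversion rate like any other. In the placebo arm, a late titre of 40 or more from an undetectable baseline counts as seroconversion whatever caused it. The trial schedules a marker that could flag infection by Day 201 and records confirmed cases, but no planned immunogenicity analysis uses either. A reader of the final tables could not tell how far the late estimates depend on infection.

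**Working it through.** **1. Does any rule remove these titres?** The documents give no figure to reproduce, so this step is a reading of the rules.

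- The PP conditions concern violations, doses, samples and windows. Infection is not named, and becoming infected breaks no stated rule.
- SAP 7.1.2.4 covers cutoffs, non-reportable results and PBMC timing. SAP 7.3 leaves missing values missing; it does not set observed values to missing.
- Protocol 13.3 makes laboratory-confirmed infection a contraindication to dose 2. Because PP from Day 42 requires both doses, confirmed infection before dose 2 is already handled in PP. Infection after dose 2 triggers nothing.
- Two partial routes out exist, both discretionary. Prohibited therapy (protocol 8.6, which includes systemic glucocorticoids and immunoglobulins) may affect set membership, so some treated COVID-19 cases could leave a set. Major protocol violations are also left undefined, so a data review could act on individual cases. Neither is an infection rule.
- COVID-19 cases can reach the adverse event tables to end of study, including unsolicited events, MAAEs and AESIs (SAP 8.3.2). The VAED terms in SAP Appendix 2 include some that are not infections, such as exposure, while SAP 7.1.3.1.3.1 limits VAED to hospitalised, laboratory-confirmed cases. No planned analysis links these tables to titres.
- In SAP 9.3 the visits marked "All Laboratory Tests" are Days 0, 3, 21, 24 and 42. Anti-N is scheduled at none of these, so this table is weak evidence of what was intended for it.

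**2. Inflation when all titres are kept.** Assumed inputs: a proportion p of the arm infected after dose 2, and a fold rise b still present at sampling. On the log scale the mean rises by p × log b, so the GMT is multiplied by b^p.

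| p | b = 2 | b = 4 | b = 8 |
|---|---|---|---|
| 5% | 1.04 | 1.07 | 1.11 |
| 10% | 1.07 | 1.15 | 1.23 |
| 20% | 1.15 | 1.32 | 1.52 |

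Any waning of the boost before sampling lowers b. For seroconversion, assume 80% without infection and that every infected subject seroconverts. The observed rate is 0.8(1 − p) + p, which gives 81%, 82% and 84% at p = 5%, 10% and 20%.

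**3. Placebo and the contrast.** The floor is 5, half the cutoff of 10 (SAP 7.1.2.3 and 7.1.2.4). The titre T after infection is assumed to be 160 to 640.

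- One infected placebo subject gives GMT = 5 × (T/5)^(1/n). With n = 25 this is 5.7 to 6.1, and seroconversion is 1/25 = 4% (Clopper-Pearson 95% CI 0.1 to 20%). With an assumed n = 10 left after withdrawals, it is 7.1 to 8.1, and seroconversion is 10% (0.3 to 45%).
- With p = 10% in both arms, the vaccine-placebo GMT ratio is multiplied by (b ÷ (T/5))^0.10. For b = 4 this is 0.81 (T = 160) or 0.71 (T = 640); for b = 8 it is 0.87 or 0.76.

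**4. Bias from excluding infected subjects.** Assume normal log10 titres and log-odds of infection that rise by s for each SD of lower titre. The GMT among the uninfected is then inflated by 10^(SD × E[Z | not infected]), where Z is the standardised log titre; I evaluated this by numerical integration. At p = 10% and s = 1.0 it is 1.11 with SD 0.5 and 1.16 with SD 0.7. With s = 0.5 and SD 0.5 it is 1.06.

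Set beside step 2 at p = 10%, exclusion at 1.11 exceeds the all-titres 1.07 (2-fold boost), and 1.16 just exceeds 1.15 (4-fold). It is smaller than 1.23 (8-fold). Either bias can be the larger, and both point upward.

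**The case against.** The all-titres result is a legitimate treatment-policy summary. SAP 2.2.2 defines persistence by GMT, seroconversion and GMFR on fixed days and promises no infection-free estimate. The study is not powered (SAP 3.4), and protocol 11.2.1 describes the group comparison as descriptive. All immunogenicity and safety data are listed, and Nab has reverse cumulative distribution and scatter plots, so infected subjects can partly be picked out by hand. In placebo, a late titre of 40 or more is itself a sign of infection. Withdrawal of placebo subjects who take public vaccination after unblinding may limit late interpretation more than retained infections do. The remedy is also imperfect: it is written after unblinding, Day 201 anti-N may not have been measured after discontinuation (SAP 10), and exclusion conditions on a post-randomisation event.

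All of this stands, and it sets the priority. It does not close the gap, because listings and plots give no estimate or interval, and nothing planned shows how far the late results depend on infection.

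A reader might infer more than the documents support:

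- *That the vaccine-placebo comparison is biased in favour of the vaccine.* With similar infection rates and the titres assumed above, it moves the other way.
- *That excluding infected subjects gives the correct answer, or at least the smaller bias.* Step 4 shows it need not.
- *That the primary results are compromised.* Days 21 and 42 leave little time for infection, and PP already handles confirmed infection before dose 2.
- *That anti-N goes wholly unreported.* SARS-CoV-2 antibody is in the safety laboratory list, and all safety data are to be listed.

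**Conclusion.** The point holds as an omission in the secondary analyses: nothing planned sets aside titres after an infection that follows dose 2, and Day 201 anti-N enters no immunogenicity rule or sensitivity analysis. If such infections occur, within-arm late GMT, GMFR and seroconversion are biased upward as measures of vaccine persistence. With none, nothing changes.

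The size cannot be fixed from the documents, which give no infection rate. The illustrative range for Group 1 is 1.04 to 1.52, across 5 to 20% infected and a 2- to 8-fold boost. Every infection rate, boost, infection titre, SD, log-odds slope and late placebo number used here is an assumption. Priority is low: a cheap improvement to consider, not a defect that invalidates the planned results.

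**What to change.** Before final lock, if that is still possible, add to SAP 8.2.2 a supplementary analysis of the late immunogenicity endpoints and leave PP and ITT unchanged:

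- Set results to missing from the first laboratory-confirmed SARS-CoV-2 infection, and set Day 201 results to missing when Day 201 anti-N is positive, where measured.
- Show it beside the all-titres analysis. Tabulate by arm the numbers infected, excluded and with Day 201 anti-N available.
- Label it as specified after the Day 42 unblinding.
- State that Day 128 has no anti-N, so exclusion there rests on reported confirmed cases and cannot clear unreported infections.
- State that exclusion conditions on a post-randomisation event and can itself bias GMT upward, so neither analysis stands alone and the pair does not bracket the truth.

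The cost is a paragraph of SAP wording, one extra set of late tables and some lost precision. With 10% of 100 subjects excluded, intervals on the log scale widen by √(1/0.9) = 1.05. The analysis also lacks the protection of pre-specification, and anti-N misses some infections and cannot date them.
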